9.8 Safety Evaluations	Vital signs description added to specify pulse/heart rate and blood pressure evaluation methods and timings, ie, at every protocol-specified visit until end of treatment
------------------------	---

Rationale: To add an external link for examples of CYP3A inhibitors and inducers; to add additional dose reduction information for CYP3A co-administration

Attachment 4 Instruction for Concomitant Medications to be Used With Precaution, Attachment 5 Inhibitors and Inducers of CYP3A	Inserted an additional link to FDA classification of CYP3A inhibitors and inducers in Attachment 4 and Attachment 5 Updated dose reduction description in Attachment 4
--	---

Attachment 1 Ibrutinib Dosing Guides, Attachment 2 Potential Dose for Younger Subjects	Added dosing tables for 330 mg/m ² , 220 mg/m ² , and 110 mg/m ² (ie, dose reductions in patients starting at 440 mg/m ²) Moved dosing table for 440 mg/m ² to Attachment 1; Attachment 2 deleted
--	--

Rationale: To improve clarity and accuracy throughout the protocol

Table 1 and Table 2 Time and Events Schedules	Added a separate Time and Events Schedule for Part 2 of the study (Table 2); removed references to Part 2 as appropriate
---	--

Table 1, Table 3, Table 4, Table 5 Time and Events Schedules, Attachment 7 Blood Volume Tables	Added and/or edited headings and footnotes for clarity
3.1 Overview of Study Design	Clarified pharmacokinetic sampling to be obtained only for subjects receiving ibrutinib in combination with background therapy in Part 2
3.1 Overview of Study Design, 6.1 Study Treatment, 9.1.4 Posttreatment Phase (Follow-up)	Clarified subjects must have completed 3 cycles of treatment to be eligible to receive ibrutinib monotherapy
Figure 2 Schematic Overview of the Study (Part 2; Randomized Part), 4.1 Inclusion Criteria	Eligibility criteria updated to specify subjects were to have received only 1 prior line of therapy for inclusion in Part 2 of the study
6 Dosage and Administration	Added reference to Investigational Product Preparation Instruction for subjects requiring dosing through a feeding tube
6.1.2 Ibrutinib Administration	Clarified methods for dispensing ibrutinib by cycle
9.2.3 Lumbar Puncture	Provided additional information for lumbar puncture and cerebral spinal fluid collection
Table 9 International Pediatric non-Hodgkin lymphomas (NHL) Response Criteria	Updated to align with guidance

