6.2.2. Ibrutinib

Treatment with ibrutinib should be temporarily stopped for any unmanageable, potentially study drug-related toxicity that is Grade \geq 3 in severity. Hematologic toxicities are expected with RICE and RVICI and it may not be feasible to determine any relationship to ibrutinib. If the hematologic toxicities are not manageable, ibrutinib should be temporarily stopped, however, if

the cytopenias can be managed with transfusion and/or growth factor support and there are no unmanageable secondary complications from these cytopenias (eg, serious infection, significant bleeding) ibrutinib may be continued, at the discretion of the investigator. Ibrutinib may be temporarily stopped for a maximum of 21 consecutive days unless reviewed and approved by the sponsor. Ibrutinib should be discontinued permanently in the event of a toxicity lasting more than 21 days. If ibrutinib is delayed or temporarily stopped, any remaining study treatment (ie, rituximab, ifosfamide, carboplatin, etoposide, vincristine, idarubicin, and dexamethasone) may be continued.

The actions in [Table 8](#) below should be taken for the following drug-related toxicities. Changes must be recorded in the Drug Accountability Records and Dosage Administration page of the electronic CRF.

- Grade 3 or greater febrile neutropenia
- Grade 4 neutropenia (ANC $<0.5 \times 10^9/L$ [ie, $<500/\text{mm}^3$]) for >14 days (after completion of CIT)
- Grade 3 thrombocytopenia (platelets $<50 \times 10^9/L$ [ie, $<50,000/\text{mm}^3$]) in the presence of significant bleeding (ie, \geq Grade 2 bleeding)
- Grade 4 thrombocytopenia (platelets $<25 \times 10^9/L$ [ie, $<25,000/\text{mm}^3$])
- Grade 3 or greater non-hematological toxicity

Table 8: Ibrutinib Dose Modifications

Occurrence of the Same Adverse Event	Action
First	Temporarily stop study drug until recovery to Grade ≤ 1 or baseline; may restart at original dose level
Second	Temporarily stop study drug until recovery to Grade ≤ 1 or baseline; restart at 25% decrease in dose (ie, 1 dose level lower) ^a
Third	Temporarily stop study drug until recovery to Grade ≤ 1 or baseline; restart at 50% decrease in dose (ie, 1 dose level lower) ^a
Fourth	Discontinue study drug

a. Consult the sponsor for calculation of the reduced dose to be administered, if needed.

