1.75 and higher		420.0	6.0	420	6	420

a. Rounded to nearest 70 mg capsule.

b. For older children, one 140-mg capsule may be substituted for each two 70-mg capsules.

Suspension and Capsule Dosing 160 mg/m²
(Full Dose Equivalent; 280 mg/1.7 m²)

Body Surface Area (m ²)		Target Dose (mg)	Suspension (70 mg/mL) Volume to be Administered (mL)	Actual Dose to Administer by Suspension (mg)	# 70 mg Capsules ^{a,b}	Actual Dose to Administer by Capsule (mg)
From	To					
0.30	0.34	48.0	0.7	49	-	-
0.35	0.39	56.0	0.8	56	-	-
0.40	0.44	64.0	0.9	63	-	-
0.45	0.49	72.0	1.0	70	-	-
0.50	0.54	80.0	1.1	77	-	-
0.55	0.59	88.0	1.3	91	-	-
0.60	0.64	96.0	1.4	98	-	-
0.65	0.69	104.0	1.5	105	-	-
0.70	0.74	112.0	1.6	112	-	-
0.75	0.79	120.0	1.7	119	2	140
0.80	0.84	128.0	1.8	126	2	140
0.85	0.89	136.0	1.9	133	2	140
0.90	0.94	144.0	2.1	147	2	140
0.95	0.99	152.0	2.2	154	2	140
1.00	1.04	160.0	2.3	161	2	140
1.05	1.09	168.0	2.4	168	2	140
1.10	1.14	176.0	2.5	175	3	210
1.15	1.19	184.0	2.6	182	3	210
1.20	1.24	192.0	2.7	189	3	210
1.25	1.29	200.0	2.9	203	3	210
1.30	1.34	208.0	3.0	210	3	210
1.35	1.39	216.0	3.1	217	3	210
1.40	1.44	224.0	3.2	224	3	210
1.45	1.49	232.0	3.3	231	3	210
1.50	1.54	240.0	3.4	238	3	210
1.55	1.59	248.0	3.5	245	4	280
1.60	1.64	256.0	3.7	259	4	280
1.65	1.69	264.0	3.8	266	4	280
1.70	1.74	272.0	3.9	273	4	280
1.75 or higher		280.0	4.0	280	4	280

a Rounded to nearest 70 mg capsule.

b For older children, one 140-mg capsule may be substituted for each two 70-mg capsules.

Suspension and Capsule Dosing 120 mg/m²
(Full Dose Equivalent; 210 mg/1.7 m²)

Body Surface Area (m ²)		Target Dose (mg)	Suspension (70 mg/mL) Volume to be Administered (mL)	Actual Dose to Administer by Suspension (mg)	# 70 mg Capsules ^{a,b}	Actual Dose to Administer by Capsule (mg)
From	To					
0.30	0.34	36.0	0.5	35	-	-
0.35	0.39	42.0	0.6	42	-	-
0.40	0.44	48.0	0.7	49	-	-
0.45	0.49	54.0	0.8	56	-	-
0.50	0.54	60.0	0.9	63	-	-
0.55	0.59	66.0	0.9	63	-	-
0.60	0.64	72.0	1.0	70	-	-
0.65	0.69	78.0	1.1	77	-	-
0.70	0.74	84.0	1.2	84	-	-
0.75	0.79	90.0	1.3	91	-	-
0.80	0.84	96.0	1.4	98	-	-
0.85	0.89	102.0	1.5	105	-	-
0.90	0.94	108.0	1.5	105	-	-
0.95	0.99	114.0	1.6	112	-	-
1.00	1.04	120.0	1.7	119	2	140
1.05	1.09	126.0	1.8	126	2	140
1.10	1.14	132.0	1.9	133	2	140
1.15	1.19	138.0	2.0	140	2	140
1.20	1.24	144.0	2.1	147	2	140
1.25	1.29	150.0	2.1	147	2	140
1.30	1.34	156.0	2.2	154	2	140
1.35	1.39	162.0	2.3	161	2	140
1.40	1.44	168.0	2.4	168	2	140
1.45	1.49	174.0	2.5	175	2	140
1.50	1.54	180.0	2.6	182	3	210
1.55	1.59	186.0	2.7	189	3	210

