1.60	1.64	192.0	2.7	189	3	210
1.65	1.69	198.0	2.8	196	3	210
1.70	1.74	204.0	2.9	203	3	210
1.75 or higher		210.0	3.0	210	3	210

a. Rounded to nearest 70 mg capsule.

b. For older children, one 140-mg capsule may be substituted for each two 70-mg capsules.

Suspension and Capsule Dosing 80 mg/m²
(Full Dose Equivalent; 140 mg/1.7 m²)

Body Surface Area (m ²)		Target Dose (mg)	Suspension (70 mg/mL) Volume to be Administered (mL)	Actual Dose to Administer by Suspension (mg)	# 70 mg Capsules ^{a,b}	Actual Dose to Administer by Capsule (mg)
From	To					
0.30	0.34	24.0	0.3	21	-	-
0.35	0.39	28.0	0.4	28	-	-
0.40	0.44	32.0	0.5	35	-	-
0.45	0.49	36.0	0.5	35	-	-
0.50	0.54	40.0	0.6	42	-	-
0.55	0.59	44.0	0.6	42	-	-
0.60	0.64	48.0	0.7	49	-	-
0.65	0.69	52.0	0.7	49	-	-
0.70	0.74	56.0	0.8	56	-	-
0.75	0.79	60.0	0.9	63	-	-
0.80	0.84	64.0	0.9	63	-	-
0.85	0.89	68.0	1.0	70	-	-
0.90	0.94	72.0	1.0	70	-	-
0.95	0.99	76.0	1.1	77	-	-
1.00	1.04	80.0	1.1	77	-	-
1.05	1.09	84.0	1.2	84	-	-
1.10	1.14	88.0	1.3	91	-	-
1.15	1.19	92.0	1.3	91	-	-
1.20	1.24	96.0	1.4	98	-	-
1.25	1.29	100.0	1.4	98	-	-
1.30	1.34	104.0	1.5	105	-	-
1.35	1.39	108.0	1.5	105	-	-
1.40	1.44	112.0	1.6	112	2	140
1.45	1.49	116.0	1.7	119	2	140
1.50	1.54	120.0	1.7	119	2	140
1.55	1.59	124.0	1.8	126	2	140
1.60	1.64	128.0	1.8	126	2	140
1.65	1.69	132.0	1.9	133	2	140
1.70	1.74	136.0	1.9	133	2	140
1.75 and higher		140.0	2.0	140	2	140

a. Rounded to nearest 70 mg capsule.

b. For older children, one 140-mg capsule may be substituted for each two 70-mg capsules.

**Suspension and Capsule Ibrutinib Dosing 440 mg/m²
(Full Dose Equivalent; 748 mg/1.7 m²)**

**NOTE: only to be used in subjects under 12 years of age-dose administered will not exceed
560 mg**

Body Surface Area (m ²)		Target Dose (mg)	Suspension (70 mg/mL) Volume to be Administered (mL)	Actual Dose to Administer by Suspension (mg)	# 70 mg Capsules ^{a,b}	Actual Dose to Administer by Capsule (mg)
From	To					
0.30	0.34	132	1.9	133	-	-
0.35	0.39	154	2.2	154	-	-
0.40	0.44	176	2.5	175	-	-
0.45	0.49	198	2.8	196	-	-
0.50	0.54	220	3.1	217	-	-
0.55	0.59	242	3.5	245	3	210
0.60	0.64	264	3.8	266	4	280
0.65	0.69	286	4.1	287	4	280
0.70	0.74	308	4.4	308	4	280
0.75	0.79	330	4.7	329	5	350
0.80	0.84	352	5.0	350	5	350
0.85	0.89	374	5.3	371	5	350
0.90	0.94	396	5.7	399	6	420
0.95	0.99	418	6.0	420	6	420
1.00	1.04	440	6.3	441	6	420
1.05	1.09	462	6.6	462	7	490
1.10	1.14	484	6.9	483	7	490
1.15	1.19	506	7.2	504	7	490
1.20	1.24	528	7.5	525	8	560
1.25	1.29	550	7.9	553	8	560
1.30	1.34	560	8.0	560	8	560

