1.35	1.39	560	8.0	560	8	560
1.40	1.44	560	8.0	560	8	560
1.45	1.49	560	8.0	560	8	560
1.50	1.54	560	8.0	560	8	560
1.55	1.59	560	8.0	560	8	560
1.60	1.64	560	8.0	560	8	560
1.65	1.69	560	8.0	560	8	560
1.70 and higher		560	8.0	560	8	560

a. Rounded to nearest 70 mg capsule.

b. For older children, one 140-mg capsule may be substituted for each two 70-mg capsules.

Suspension and Capsule Dosing 330 mg/m²
(Full Dose Equivalent; 561 mg/1.7 m²)

Body Surface Area (m ²)	Target Dose (mg)	Suspension (70 mg/mL) Volume to be Administered (mL)	Actual Dose to Administer by Suspension (mg)	# 70 mg Capsules ^{a,b}	Actual Dose to Administer by Capsule (mg)
From	To				
0.30	0.34	99.0	1.4	98	-
0.35	0.39	115.5	1.7	119	-
0.40	0.44	132.0	1.9	133	-
0.45	0.49	148.5	2.1	147	-
0.50	0.54	165.0	2.4	168	-
0.55	0.59	181.5	2.6	182	-
0.60	0.64	198.0	2.8	196	3
0.65	0.69	214.5	3.1	217	3
0.70	0.74	231.0	3.3	231	3
0.75	0.79	247.5	3.5	245	3
0.80	0.84	264.0	3.8	266	4
0.85	0.89	280.5	4.0	280	4
0.90	0.94	297.0	4.2	294	4
0.95	0.99	313.5	4.5	315	4
1.00	1.04	330.0	4.7	329	5
1.05	1.09	346.5	5.0	350	5
1.10	1.14	363.0	5.2	364	5
1.15	1.19	379.5	5.4	378	5
1.20	1.24	396.0	5.7	399	6
1.25	1.29	412.5	5.9	413	6
1.30	1.34	429.0	6.1	427	6
1.35	1.39	445.5	6.4	448	6
1.40	1.44	462.0	6.6	462	7
1.45	1.49	478.5	6.8	476	7
1.50	1.54	495.0	7.1	497	7
1.55	1.59	511.5	7.3	511	7
1.60	1.64	528.0	7.5	525	8
1.65	1.69	544.5	7.8	546	8
1.70 and higher	560.0	8.0	560	8	560

a. Rounded to nearest 70 mg capsule.

b. For older children, one 140-mg capsule may be substituted for each two 70-mg capsules.

Suspension and Capsule Dosing 220 mg/m²
(Full Dose Equivalent; 374 mg/1.7 m²)

Body Surface Area (m ²)	Target Dose (mg)	Suspension (70 mg/mL) Volume to be Administered (mL)	Actual Dose to Administer by Suspension (mg)	# 70 mg Capsules ^{a,b}	Actual Dose to Administer by Capsule (mg)
From	To				
0.30	0.34	66.0	0.9	63	-
0.35	0.39	77.0	1.1	77	-
0.40	0.44	88.0	1.3	91	-
0.45	0.49	99.0	1.4	98	-
0.50	0.54	110.0	1.6	112	-
0.55	0.59	121.0	1.7	119	-
0.60	0.64	132.0	1.9	133	2
0.65	0.69	143.0	2.0	140	2
0.70	0.74	154.0	2.2	154	2
0.75	0.79	165.0	2.4	168	2
0.80	0.84	176.0	2.5	175	3
0.85	0.89	187.0	2.7	189	3
0.90	0.94	198.0	2.8	196	3
0.95	0.99	209.0	3.0	210	3
1.00	1.04	220.0	3.1	217	3
1.05	1.09	231.0	3.3	231	3
1.10	1.14	242.0	3.5	245	3
1.15	1.19	253.0	3.6	252	4
1.20	1.24	264.0	3.8	266	4
1.25	1.29	275.0	3.9	273	4
1.30	1.34	286.0	4.1	287	4
1.35	1.39	297.0	4.2	294	4
1.40	1.44	308.0	4.4	308	4
1.45	1.49	319.0	4.6	322	5
1.50	1.54	330.0	4.7	329	5

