1.55	1.59	341.0	4.9	343	5
1.60	1.64	352.0	5.0	350	5
1.65	1.69	363.0	5.2	364	5
1.70	1.74	374.0	5.3	371	5
1.75 and higher	385.0	5.5	385	6	420

a. Rounded to nearest 70 mg capsule.

b. For older children, one 140-mg capsule may be substituted for each two 70-mg capsules.

**Suspension and Capsule Dosing 110 mg/m²
(Full Dose Equivalent; 187 mg/1.7 m²)**

Body Surface Area (m ²)	Target Dose (mg)	Suspension (70 mg/mL) Volume to be Administered (mL)	Actual Dose to Administer by Suspension (mg)	# 70 mg Capsules ^{a,b}	Actual Dose to Administer by Capsule (mg)
From	To				
0.30	0.34	33.0	0.5	35	-
0.35	0.39	38.5	0.6	42	-
0.40	0.44	44.0	0.6	42	-
0.45	0.49	49.5	0.7	49	-
0.50	0.54	55.0	0.8	56	-
0.55	0.59	60.5	0.9	63	-
0.60	0.64	66.0	0.9	63	1
0.65	0.69	71.5	1.0	70	1
0.70	0.74	77.0	1.1	77	1
0.75	0.79	82.5	1.2	84	1
0.80	0.84	88.0	1.3	91	1
0.85	0.89	93.5	1.3	91	1
0.90	0.94	99.0	1.4	98	1
0.95	0.99	104.5	1.5	105	1
1.00	1.04	110.0	1.6	112	2
1.05	1.09	115.5	1.7	119	2
1.10	1.14	121.0	1.7	119	2
1.15	1.19	126.5	1.8	126	2
1.20	1.24	132.0	1.9	133	2
1.25	1.29	137.5	2.0	140	2
1.30	1.34	143.0	2.0	140	2
1.35	1.39	148.5	2.1	147	2
1.40	1.44	154.0	2.2	154	2
1.45	1.49	159.5	2.3	161	2
1.50	1.54	165.0	2.4	168	2
1.55	1.59	170.5	2.4	168	2
1.60	1.64	176.0	2.5	175	3
1.65	1.69	181.5	2.6	182	3
1.70	1.74	187.0	2.7	189	3
1.75 and higher		192.5	2.8	196	3

a. Rounded to nearest 70 mg capsule.

b. For older children, one 140-mg capsule may be substituted for each two 70-mg capsules.

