Attachment 4: Instruction for Concomitant Medications to be Used With Precaution

Ibrutinib is metabolized primarily by CYP3A. Avoid co-administration with strong or moderate CYP3A inhibitors and consider alternative agents with less CYP3A inhibition. Co-administration of ketoconazole, a strong CYP3A inhibitor, in 18 healthy subjects increased dose normalized exposure, C_{max} and AUC₀-last, of ibrutinib by 29- and 24-fold, respectively. A DDI study in patients with B-cell malignancies (PCI-32765LYM1003) found that co-administration of ibrutinib with the moderate CYP3A inhibitors erythromycin and voriconazole, increased C_{max} by 3.4-fold and 6.7-fold and increased AUC by 3.0-fold and 5.7-fold, respectively. Clinical safety data in 66 subjects treated with moderate (n=47) or strong CYP3A inhibitors (n=19) did not reveal meaningful increases in toxicities. Strong inhibitors of CYP3A (eg, ketoconazole, indinavir, nelfinavir, ritonavir, saquinavir, clarithromycin, telithromycin, itraconazole, nefazadone, and cobicistat) and moderate inhibitors (eg, voriconazole, erythromycin, amprenavir, aprepitant, atazanavir, ciprofloxacin, crizotinib, darunavir/ritonavir, diltiazem, fluconazole, fosamprenavir, imatinib, verapamil, amiodarone, dronedarone) should be avoided. If the benefit outweighs the risk and a strong CYP3A inhibitor must be used, reduce the ibrutinib dose by 75% (140 mg/1.7 m² rounded down to 80 mg/m² for starting dose of 329 mg/m² or to 110 mg/m² for dose of 440 mg/m²) or stop treatment temporarily (for 7 days or less). If a moderate CYP3A inhibitor must be used, reduce ibrutinib by 75% (140 mg/1.7 m² rounded down to 80 mg/m² for starting dose of 329 mg/m² or to 110 mg/m² for dose of 440 mg/m²) for the duration of the inhibitor use. No dose adjustment is required in combination with mild inhibitors. Monitor the subject closely for toxicity and follow dose modification guidance as needed. Avoid grapefruit and Seville oranges during ibrutinib treatment, as these contain moderate inhibitors of CYP3A.

Co-administration of ibrutinib with strong inducers of CYP3A decreases ibrutinib plasma concentrations by up to 90%. Avoid concomitant use of strong CYP3A inducers (eg, carbamazepine, rifampin, phenytoin, and St. John's Wort). Consider alternative agents with less CYP3A induction.

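### For under-12s on 440 mg/m² held at the 560 mg cap, the dose-reduction tables do not carry the cap down, so most printed reductions fall short and the largest children get no first-step reduction

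*Protocol*

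**What the plan says.** Table 8 (protocol Section 6.2.2) sets the response to repeated occurrences of the same drug-related toxicity. After the first, the original dose may be resumed. After the second, the instruction is to "restart at 25% decrease in dose (ie, 1 dose level lower"). After the third it is a 50% decrease, and after the fourth ibrutinib stops. The text below Table 8 refers sites to Attachment 1 for BSA-based dosing and rounding.

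Attachment 4 requires a 75% reduction when a moderate or strong CYP3A inhibitor must be used; for a strong inhibitor, a stop of up to 7 days is the alternative. It gives the reduced level as "to 110 mg/m² for dose of 440 mg/m²".

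The note above the 440 mg/m² table in Attachment 1 says it is "only to be used in subjects under 12 years of age-dose administered will not exceed" 560 mg, and the table prints 560 mg in every row from BSA 1.30. The Amendment 5 entry in the amendment log is used here only for the purpose of the 330, 220 and 110 mg/m² tables: "dose reductions in patients starting at 440 mg/m"².

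In these tables the columns are BSA, target mg, suspension mL, suspension mg, number of 70 mg capsules and, where it survives extraction, capsule mg.
- The last row of the 330 table reads "1.70 and higher 560.0 8.0 560 8 560". Its first row with 8 capsules is "1.60 1.64 528.0 7.5 525 8".
- The last row of the 220 table is "1.75 and higher 385.0 5.5 385 6 420".
- In the family that starts at 329 mg/m², the 240 table ends at "420.0 6.0 420 6 420".

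**The concern.** A percentage reduction has to be taken from the dose the child is actually receiving. From BSA 1.30 that dose is a flat 560 mg, but the reduction tables go on multiplying BSA by 330, 220 or 110 as if the starting dose were not capped. The shortfall therefore grows with body size.

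At the top of the 330 table, a child who has just had a second episode of the same listed toxicity is restarted on an unchanged dose. On capsules at BSA 1.75 and above, the printed sequence is 560, 560, 420 mg and then discontinuation. The 50% step is never delivered, and the child goes through a further toxicity before any reduction. With a CYP3A inhibitor, the child gets more drug than the 75% rule allows at the time when exposure is already raised.

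**Working it through.** **Inputs.** Stated cuts come from Table 8 (25%, 50%) and Attachment 4 (75%). Printed doses come from the 440, 330, 220 and 110 mg/m² tables in Attachment 1. Capsule mg = number of capsules × 70.

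**Reproducing the printed targets.** Target = lower BSA bound × mg/m², with a 560 mg ceiling in the 440 and 330 tables. All targets from BSA 1.20 up reproduce; for example, 330 × 1.60 = 528.0 and 220 × 1.75 = 385.0. The multiplication is right. The question is what the rows deliver against the capped starting dose.

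**Correct doses in capped rows (BSA 1.30 and above).** 560 × 0.75 = 420 mg; 560 × 0.50 = 280 mg; 560 × 0.25 = 140 mg.

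**Printed cut = 1 − printed dose / 560.** Each cell gives suspension mg (cut) / capsule mg (cut).

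| BSA from | 330 table, stated 25% | 220 table, stated 50% | 110 table, stated 75% |
|---|---|---|---|
| 1.30 | 427 (23.75%) / 420 (25%) | 287 (48.75%) / 280 (50%) | 140 (75%) / 140 (75%) |
| 1.35 | 448 (20%) / 420 (25%) | 294 (47.5%) / 280 (50%) | 147 (73.75%) / 140 (75%) |
| 1.40 | 462 (17.5%) / 490 (12.5%) | 308 (45%) / 280 (50%) | 154 (72.5%) / 140 (75%) |
| 1.45 | 476 (15%) / 490 (12.5%) | 322 (42.5%) / 350 (37.5%) | 161 (71.25%) / 140 (75%) |
| 1.50 | 497 (11.25%) / 490 (12.5%) | 329 (41.25%) / 350 (37.5%) | 168 (70%) / 140 (75%) |
| 1.55 | 511 (8.75%) / 490 (12.5%) | 343 (38.75%) / 350 (37.5%) | 168 (70%) / 140 (75%) |
| 1.60 | 525 (6.25%) / 560 (0%) | 350 (37.5%) / 350 (37.5%) | 175 (68.75%) / 210 (62.5%) |
| 1.65 | 546 (2.5%) / 560 (0%) | 364 (35%) / 350 (37.5%) | 182 (67.5%) / 210 (62.5%) |
| 1.70 | 560 (0%) / 560 (0%) | 371 (33.75%) / 350 (37.5%) | 189 (66.25%) / 210 (62.5%) |
| 1.75 and above | (same row as 1.70) | 385 (31.25%) / 420 (25%) | 196 (65%) / 210 (62.5%) |

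**Rows below the stated cut.**
- Suspension: 9 of 9, 10 of 10 and 9 of 10, so 28 of 29.
- Capsule: 7 of 9, 7 of 10 and 4 of 10, so 18 of 29.
- Unrounded targets: 29 of 29. Rounding is therefore not the cause.
- Below BSA 1.30 the unrounded targets give exactly 25%, 50% and 75%.

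**Excess over the correct dose in the top row.**
- First step: 560/420 = +33%.
- Second step: 385/280 = +37.5% by suspension; 420/280 = +50% by capsule.
- CYP3A step: 196/140 = +40% by suspension; 210/140 = +50% by capsule.

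**Comparison with the 329 mg/m² family.** Its 240, 160 and 80 tables stop at 420, 280 and 140 mg, which are exactly 75%, 50% and 25% of 560 mg. By suspension, a subject capped at 560 mg with BSA 1.70–1.74 gets 406, 273 and 133 mg, cuts of 27.5%, 51.25% and 76.25%. At 1.75 and above the cuts are 25%, 50% and 75%. No capped subject gets less than the stated cut.

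**Body size.** With the Attachment 3 formula and an assumed height of 150 cm, weight = BSA² × 3600/150. BSA 1.30, 1.40, 1.60, 1.70 and 1.75 correspond to 40.6, 47.0, 61.4, 69.4 and 73.5 kg.

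**Illustrative exposure with an inhibitor.** Attachment 4 reports a 5.7-fold AUC increase with voriconazole. Assuming dose-proportional kinetics and that this ratio applies in children, exposure relative to uninhibited 560 mg is 5.7 × 140/560 = 1.4 with a true 75% cut. It is 5.7 × 196/560 = 2.0 and 5.7 × 210/560 = 2.1 with the top-row doses.

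**The case against.** The strongest objections concern consequence, because the arithmetic is not in dispute.

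- **Sponsor footnote.** Both reduction rows of Table 8 carry a footnote telling sites to consult the sponsor on the reduced dose if needed. A site that sees 8 capsules before and 8 after might well ask. This lowers the risk, but the step is discretionary, and a table printing a definite mg, mL and capsule count gives little reason to use it.
- **Dose-level reading.** One level below 440 mg/m² is nominally 330 mg/m². But Table 8 equates one level with a 25% decrease, and 560 to 560 mg is no decrease on any reading.
- **Small shortfalls.** Some suspension rows miss by only 7 mg, or 0.1 mL (427 against 420, 287 against 280, 147 against 140), and in the 110 table most capped capsule rows are correct. Both points stand, and the row counts should be read with them in mind. They do not explain a gap that widens steadily with BSA. Capsule rounding elsewhere, such as 350 to 280 mg (a 20% cut) at BSA 1.10 in the 329 family, is a separate matter of 70 mg units.
- **Few patients, little time.** Ibrutinib runs for at most six 28-day cycles without delays, or 168 days. If the last subject entered around 20 July 2020, scheduled dosing ends about 4 January 2021, some 16 weeks after Amendment 6 (15 September 2020). A formal amendment could arrive too late, which favors a dosing letter.
- **Weak exposure–toxicity link.** Section 1.3.2 reports no meaningful relationship of bleeding or infection with exposure, and no dose-limiting toxicity up to 840 mg with RICE in adults. This tempers the likely harm, but these are adult data and they do not justify tables that contradict the protocol's own reduction rule.

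**Conclusion.** The concern holds as stated. For children under 12 on 440 mg/m² with BSA 1.30 or more, Attachment 1 does not deliver the 25%, 50% and 75% reductions that Table 8 and Attachment 4 require. At the extreme, the first step is no reduction (BSA 1.70 and above, or 1.60 and above by capsule), the second is 31.25% (25% by capsule) and the CYP3A step is 65% (62.5% by capsule). The 329 mg/m² family has the same 560 mg ceiling and carries it down, so this looks like an omission and not a design choice.

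The dose figures rest only on printed rows; the weights assume a height of 150 cm. The affected group is narrow and the documents do not say how many children fall in it. It remains relevant because Section 17.9.1 lets ongoing patients continue study treatment. It should be fixed, but it does not affect the primary analysis.

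**What to change.** In Attachment 1, for BSA 1.30 m² and above, cap the three reduction tables as follows:

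| Table | Maximum dose | Suspension | 70 mg capsules | Cut from 560 mg |
|---|---|---|---|---|
| 330 mg/m² | 420 mg | 6.0 mL | 6 | 25% |
| 220 mg/m² | 280 mg | 4.0 mL | 4 | 50% |
| 110 mg/m² | 140 mg | 2.0 mL | 2 | 75% |

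These cuts are exact in both formulations. Leave the rows below 1.30 with their ordinary capsule rounding. Send the corrected rows, by amendment or the quicker dosing letter, to sites with subjects still on ibrutinib. As an optional safeguard, check any recorded dose reduction in a subject on 440 mg/m² against the mg actually given.

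The cost is corrected rows in three tables and one communication to sites, with no new data and no change to the analysis.
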